Neuroimaging Procedures: Functional MRI (fMRI) data will be acquired from all participants 1 week before and within 3 weeks of completion of the 11-session CBT protocol. The scans will be conducted at the MUSC Center for Biomedical Imaging, which is also designated as VA-approved space. High-resolution structural scans will be obtained at the beginning of each session using an inversion recovery 3D spoiled gradient echo (3DSPGR) sequence, 128 slices, matrix size: 256 x 256, field of view: 24 cm, section thickness: 1.5 mm with no gap between sections, giving an in-plane resolution of 0.94 mm. This sequence will be used for anatomic overlays of the functional data, for spatial normalization to a standard atlas, and subsequent voxel-based morphometry (beyond the scope of this proposal). Outside the scanner, participants will undergo a thermal method-of-limits procedure (aided by parameter estimation by sequential testing) to determine the temperature output required from the Medoc Pathway System to reliably produce a subjective NRS pain rating of 7/10. This temperature will be delivered in 12-second tonic blocks interspersed with 18-second rest/pain rating periods during the fMRI sequence. The data will be preprocessed in accordance with standard practice in our laboratory using SPM 8 (Wellcome Department of Cognitive Neurology, London, UK) and the average time courses from anatomically defined regions of interest (ROIs) extracted and analyzed using customized scripts (Matlab 6.5, Mathworks, Natick, MD).

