Randomization: We will stratify randomization by (1) severity of opiate use (COMM score) and (2) pain severity (BPI score). Urn randomization will be used to balance the randomization assignment with respect to these strata. The purpose of stratification is to distribute these potential prognostic factors equally across treatment groups.

Intent-to-Treat Analyses. All analyses will be performed on two samples: (1) the intent-to-treat sample consisting of all randomized subjects and (2) the completers sample consisting of all subjects who complete at least 7 out of 11 sessions.

Missing Data. We will perform attrition analyses on whether participants and dropouts differ on key variables (symptom severity) and whether variables on which they differ interact with treatments to affect outcome measures. As participants will be randomized to treatment, it is unlikely that missing data will produce biased estimates of treatment effect, as observed and unobserved covariates should theoretically be balanced across treatment groups. In addition, in general, less than 10% missing data have little impact upon study power and do not introduce bias, regardless of the missing data mechanism.⁷⁴ Larger proportions of data missing at random (MAR) or missing not at random (MNAR) could potentially bias study findings and reduce power. If the percent missing data are greater than 10%, propensity score methods will be used for data imputation. In the propensity score method, first the distribution of the missing indicator variable given the observed data is modeled to derive a propensity score. Then observations are grouped on these propensity scores and an approximate Bayesian bootstrap imputation is applied to each group.

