Time-Series Variables: The actigraphy devices will yield time-series data including sleep latency, total sleep time and sleep efficiency. Hierarchical Linear Modeling (HLM) will be applied to evaluate daily (time-series) pain, craving, opiate used, mood, anxiety, and physical activity ratings throughout the 3 phases of the study (baseline, treatment, and follow-up) and by group. The covariance structure of the model will be set to first-order autoregressive and independent effects of treatment on average daily pain will be assessed by controlling for daily fluctuations in craving, mood, anxiety, and activity in the model. Additional co-variates of CBT-related effects will include therapeutic alliance and pain coping styles. Additionally, cross-lag correlational analyses will be conducted on pain, craving, mood, anxiety, and activity data to estimate temporal order of changes during the trial.

Repeated Measures Variables: BPI, COMM, as well as mean weekly sleep latency, total sleep time and sleep efficiency scores will be examined with HLM using an unstructured covariance matrix. Subject-level intercepts will be entered into the model at level-1, and a time X group (real vs. sham tDCS) mixed model will be implemented. The primary model parameter of interest will be the time X group interaction term; however, main effects will be specified in the model. Effects of treatment on pain and opioid misuse will be separated from mood effects by co-varying mood and anxiety ratings at the individual subject-level.

Power: Effect sizes (Cohen's d) for CBT for chronic pain range from 0.3 to 1.4. A realistic effect-size estimate for the CBT intervention would be categorized as "medium/modest" (d=.5). The effect-size associated with clinical effects of tDCS on chronic pain in the current literature is also medium/modest (d=.5). With 150 subjects (75 in each group), power to detect effects (alpha=.05, effect-size d=.5, r among repeated measures=.5) is good to excellent (1- β = .80 and .99, respectively). Power will be higher for the HLM model as sources of intra-class variability are better managed.

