Hypothesis 2a: CBT + real tDCS will result in significantly greater reductions, as compared to CBT + sham tDCS, in COMM scores and opiate craving ratings (electronic diary) compared to CBT + sham tDCS. To test this hypothesis, time-series analysis of diary ratings of opiate cravings will be conducted and COMM total scores will be used as repeated measures variables using the HLM methods and co-variate strategies delineated above.

Hypothesis 2b: CBT + real tDCS will result in significantly greater reductions, as compared to CBT + sham tDCS, in depression (BDI-II), anxiety (BAI), PTSD (PCL-M) and sleep (PSQI). To test this hypothesis, total scores on the identified measurements will be used as repeated measures variables using the HLM methods and co-variate strategies delineated above.

Hypothesis 2c: Total sleep time will mediate the clinical benefits of combined CBT-tDCS on chronic pain. To test this, structural equation modeling (SEM) will be used to examine the amount of variance explained in clinical improvement related to tDCS+CBT with and without total sleep time entered into the temporally dynamic model.

Hypothesis 3a: At baseline, percent BOLD signal change in the left DLPFC during pain blocks will be inversely related to BOLD signal in the left insula, ACC, thalamus, caudate, putamen, and medial prefrontal cortex.

Hypothesis 3b: After treatment, percent BOLD signal change in the left DLPFC during pain blocks will be significantly greater in the CBT + real tDCS group as compared to CBT + sham tDCS.

Hypothesis 3c: Functional connectivity between the left DLPFC and insula and ACC after treatment will be greater in participants who receive CBT + real tDCS as compared to CBT + sham tDCS.

Hypothesis 3d: The change in functional connectivity will be correlated with changes in pain (BPI), opiate use severity (COMM), and total sleep time.

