For hypotheses 3a-3d, we will measure the following dependent variables: (1) percent change in BOLD signal in the left DLPFC as well as other limbic and executive regions of interest (ROIs) including the left and right insula, ACC, thalamus, caudate, putamen, and medial prefrontal cortex; and (2) functional connectivity (quantified as the average correlation coefficient between the ROIs) between the left DLPFC and the aforementioned ROIs will be used to test the hypothesis that CBT and tDCS have a synergistic effect on the neural adaptations in pain-control circuitry (i.e., insula and ACC). We will also investigate the functional connectivity with a negative control region (i.e., the primary visual cortex), which should not be differentially

modulated by either tDCS or CBT treatment. Group analyses will be performed using a random effects model (corrected, $p<0.01$ cluster level, $k= 25$, SPM 8).

Hypothesis 3e: Functional connectivity between the left DLPFC and insula and ACC after treatment will be greater in participants who receive CBT + real tDCS as compared to CBT + sham tDCS, and the change in functional connectivity will be correlated with changes in total sleep time.

HUMAN SUBJECTS RESEARCH

Protection of Human Subjects

Risks to Subjects

[name] is a licensed clinical psychologist with extensive training and experience in conducting human research. The Co-Is also have extensive experience in human research, and Drs. [name], [name], [name], [name], [name], [name], [name], and [name] have all completed the University of Miami computer-based CITI Human Subjects Research Education Course. All research activity, informed consents, and continuing reviews will be reviewed by MUSC's IRB in compliance with 45CFR46 before the research is started and continuing review will occur annually. The research staff will ensure that all information needed for the continuing review is at the IRB in accordance with IRB requirements.

Human Subjects Involvement and Characteristics

A total of 150 adults between the ages of 18 and 70 will be recruited over a 5-year period. The inclusion/exclusion criteria for the study are as follows:

Inclusion Criteria:

1. Ages 18 to 70.
2. United States Veteran or family member of a Veteran.
3. Able to provide informed consent and function at an intellectual level sufficient to allow accurate completion of the assessment instruments.
4. Subjects must be able to comprehend English.

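### The real-versus-sham fMRI comparisons (H3b, H3c, first clause of H3e) are worded as post-treatment levels, and the plan does not say that the pre-treatment scan enters them; adjusting for it would gain precision at almost no cost

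*Combined protocol and SAP*

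**What the plan says.** Neuroimaging Procedures sets two scans for everyone: "Functional MRI (fMRI) data will be acquired from all participants 1 week before and within 3 weeks of completion of the 11-session CBT protocol".

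Under Hypotheses, the imaging arm comparisons are stated at one time point. H3b: "After treatment, percent BOLD signal change in the left DLPFC during pain blocks will be significantly greater in the CBT + real tDCS group". H3c: "Functional connectivity between the left DLPFC and insula and ACC after treatment will be greater in participants who receive CBT + real tDCS". The first clause of H3e repeats H3c. The signal change in H3b is a within-scan contrast, not a change from before to after treatment: H3a uses the same measure at baseline alone.

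The pre-treatment scan has two stated uses. One is H3a, which is baseline only. The other is the correlations of change. H3d: "The change in functional connectivity will be correlated with changes in pain (BPI), opiate use severity (COMM), and total sleep time"; and the second clause of H3e: "and the change in functional connectivity will be correlated with changes in total sleep time". Neither compares the arms.

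On the model, the paragraph after H3d says only: "Group analyses will be performed using a random effects model". The time-by-group model under Repeated Measures Variables is given for other outcomes: "BPI, COMM, as well as mean weekly sleep latency, total sleep time and sleep efficiency scores will be examined with HLM". H1a, H1b, H2a and H2b refer back to those HLM methods; H3a to H3e do not. Randomization names two balancing factors: "We will stratify randomization by (1) severity of opiate use (COMM score) and (2) pain severity (BPI score".

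**The concern.** People differ in their BOLD response to pain and in connectivity, and some of that difference persists from one scan to the next. A comparison of post-treatment values alone leaves all of it in the error term. Adjusting for the first scan removes the part that the two scans share.

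The urn balances COMM and BPI, not imaging measures. If the arms happen to differ at baseline in left DLPFC response, a post-only comparison carries part of that difference into the estimated effect of tDCS, with no correction. What is at stake is the sensitivity of Aim 3 and how far readers can trust its result in the allocation actually obtained.

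**Working it through.** **The plan's own fMRI power figure.** The Power section gives .80 with 12 per group, effect size 1.8, two-tailed alpha .01. A two-sample t calculation has noncentrality 1.8/√(2/12) = 4.41 and gives .93; .80 is reached at about 9 per group. The figure does not reproduce, and the variance components behind it are not printed. In any case it concerns pain minus rest, not real versus sham, so it does not bear on the arm comparisons.

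**Inputs.**
- 75 per arm (Power), assuming that nobody is lost before the second scan.
- Two-sided alpha .01 (fMRI power paragraph), and .05 (Data Management and Analysis, for primary hypotheses) as the alternative. The plan does not say which applies to an ROI arm comparison.
- d = .5: assumed. It is the plan's clinical tDCS figure; no between-arm fMRI effect is given.
- Pre-post correlation r = .3, .5, .7: assumed. The plan gives .5 for its clinical power calculation and nothing for fMRI.

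**Precision.** In SD units, SE of the post-only arm difference = √(2/75) = .163. Its variance is multiplied by (1 − r²) under ANCOVA and by 2(1 − r) for an unadjusted change score. Noncentrality is .5/.163 = 3.06 post-only. Under ANCOVA it is 3.06/√(1 − r²) = 3.21, 3.54 and 4.29. Power is by noncentral t. The difference detectable with 80% power at alpha .01 uses the normal approximation, (2.576 + .842) × .163 × √(1 − r²). The post-only sample of equal precision is 75/(1 − r²).

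| | Post-only | ANCOVA r = .3 | r = .5 | r = .7 |
|---|---|---|---|---|
| Variance reduction | – | 9% | 25% | 49% |
| Equivalent post-only n per arm | 75 | 82 | 100 | 147 |
| Power, alpha .01 | .674 | .725 | .821 | .952 |
| Power, alpha .05 | .860 | .890 | .940 | .989 |
| Detectable difference (SD), alpha .01 | .56 | .53 | .48 | .40 |

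An unadjusted change score at alpha .01 has power .49, .67 and .91 for the same r. It is more precise than post-only only when 2(1 − r) < 1, that is, r > .5.

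**Chance baseline imbalance.** The SE of a baseline difference is also .163 SD, so 95% of allocations fall within ±.32 SD for a given measure. A difference beyond .3 SD in either direction has probability 2 × [1 − Φ(.3/.163)] = .066; half of that, .033, favours real tDCS if a higher value does. Post-only passes on r times the imbalance. For an imbalance of 2 SE (.33 SD), the shift is .10, .16 and .23 SD at r = .3, .5 and .7.

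With no true effect, the post-treatment z given a baseline z of 2 is normal with mean 2r and variance 1 − r². The chance that it exceeds ±2.576 is .020, .034 and .050. Averaged over all randomisations the rate stays at the nominal .01 (simulated: .0098 to .0099).

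**The case against.** **The model may include baseline.** H3b and H3c say when the arms should differ, not what enters the model, and a random effects model neither includes nor excludes a baseline term. Nearby text leans towards change: the section on brain pathways and CBT speaks of imaging before and after treatment, and the paragraph after H3d speaks of neural adaptations. This stands as a limit. Post-only is a reading of the hypotheses, and the plan does not rule out adjustment. But nothing in it supplies the adjustment either, so the wording is needed in both cases.

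**Bias.** A reader might infer that post-only comparison makes chance imbalance pass for a tDCS effect, or inflates type I error. The documents do not support that. Allocation is randomised, so the test is unbiased on average with its nominal alpha. Only the fraction r of an imbalance carries through, and the raised error rates above are conditional on an unusual allocation.

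**Different scales.** A reader might also infer that H3e contradicts itself by pairing a post-treatment contrast with a correlation of change. It does not. Under randomisation the arm difference after treatment and the arm difference in change have the same expectation and units, and the correlation asks a different question.

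**Size.** The gain may be small. Pain temperature is set individually to give a rating of 7 out of 10, and the scans are roughly three months apart, so a low r is plausible. At r = .3 the gain is about five points of power at alpha .01 and three at .05. This stands; the size is unknown until r is known.

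**Conclusion.** The concern holds as a gap in specification with a cost in precision. As worded, the imaging arm comparisons leave unused a baseline measurement that is planned for every participant. The cost runs from slight (r = .3) to the equivalent of nearly doubling the sample (r = .7: 147 against 75 per arm). These figures rest on an assumed d, an assumed r and complete second scans; missing scans would lower every power figure. The imbalance point is secondary and conditional on the allocation obtained. The statement that the test is unbiased refers to the randomised sample. The pain, opioid and sleep analyses are untouched.

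**What to change.** For H3b, H3c and the arm comparison in H3e, state that arms are compared on the post-treatment ROI or connectivity value by ANCOVA, or by a mixed model with baseline means constrained equal. Adjust for the same measure at the pre-treatment scan and for the two urn factors, COMM and BPI. Do not use an unadjusted change score for the arm comparison: at r = .3 its power at alpha .01 is .49, below the .67 of post-only. State the alpha that applies to these tests. The correlations of change in H3d and H3e can stay as they are.

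The cost is SAP wording and a few degrees of freedom; both scans are already planned. The change should be made before the imaging data are analysed by arm.

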fMRI power to detect effects for planned contrasts was estimated as function of N, mean difference in percent signal change between block/conditions (μ_D), within-subject variability over time (σ_W), and between subject variability (σ_B) based on previous work conducted by our group. The effect size for our previously employed pain minus rest contrast was 1.8. Thus, power (1- β) reaches .80 with only 12 participants per group (two-tailed, alpha=.01). The present study is therefore well-powered to identify significant connectivity and activation patterns using the pain-rest block paradigm and functional connectivity methods proposed.

Hypotheses: The hypotheses and statistical approaches for testing each hypothesis is as follows:

Hypothesis 1a: CBT + real tDCS will result in significantly greater improvements, as compared to CBT + sham tDCS, in average daily pain (electronic diary), pain unpleasantness (electronic diary) and functional impairment due to pain (BPI). To test this hypothesis, time-series analysis of diary average pain and pain-unpleasantness ratings will be conducted and BPI total scores will be used as repeated measures variables using the HLM methods and model co-variate strategies delineated above.

Hypothesis 1b: CBT + real tDCS will result in significantly greater improvement, as compared to CBT + sham tDCS, in sleep latency, total sleep time and sleep efficiency. To test this hypothesis, time-series analysis of actigraphy sleep latency, total sleep time and sleep efficiency values will be used as repeated measures variables using the HLM methods and model co-variate strategies delineated above.

Hypothesis 1c: Sleep latency, total sleep time, and sleep efficiency will improve significantly after the manualized CBT module devoted to sleep hygiene compared to other CBT modules. To test this hypothesis, interrupted time-series analysis (via HLM) will be conducted with the "Sleep Hygiene" CBT module established as the temporal demarcation point.

Hypothesis 1d: Time-series data representing sleep latency, total sleep time and sleep efficiency *improvements will lead* any observed *improvements* in pain and functioning consistent with emerging data on the temporal relationship between sleep and pain.⁷⁹ To test this hypothesis, lead-lag analysis of key time-series variables (sleep latency, total sleep time and sleep efficiency, pain and functional impairment due to pain) will be conducted.

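### Hypotheses 3d and 3e correlate change in connectivity with clinical change and state no term for arm, so a simple correlation would mix the arm effects with any association within arms.

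*Combined protocol and SAP*

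**What the plan says.** The Hypotheses part of Statistical Analyses and Power opens with the promise "The hypotheses and statistical approaches for testing each hypothesis is as follows". For Hypothesis 3d the whole statement is "The change in functional connectivity will be correlated with changes in pain (BPI), opiate use severity (COMM), and total sleep time". Hypothesis 3e adds that "the change in functional connectivity will be correlated with changes in total sleep time". No test, arm covariate or within-arm analysis is named for either.

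The paragraph that follows Hypothesis 3d defines the imaging variables for 3a-3d and adds "Group analyses will be performed using a random effects model", with a cluster-level threshold. It does not say whether arm enters the correlation between connectivity and clinical change. The time-by-group mixed model described under Repeated Measures Variables is called on for Hypotheses 1a, 1b, 2a and 2b, but not for 3d or 3e.

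The plan also predicts arm differences on both sides of the correlation. Hypothesis 3c states: "Functional connectivity between the left DLPFC and insula and ACC after treatment will be greater in participants who receive CBT + real tDCS". Hypotheses 1a, 1b and 2a predict greater improvement under real tDCS in BPI, total sleep time and COMM respectively.

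**The concern.** If real tDCS raises connectivity and also improves an outcome, the two arms form two clouds of points, one displaced from the other in both directions. A correlation over all participants then picks up the displacement, even if connectivity change says nothing about who improves within an arm. The sign is the one the trial would hope for: negative with BPI and COMM, positive with total sleep time.

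Hypotheses 3d and 3e are where the plan ties neural change to clinical change, which Specific Aim 3 asks for. A significant simple correlation could partly restate Hypothesis 3c together with 1a, 1b or 2a. It would not separate two readings: that participants whose connectivity changed more improved more, or that the real-tDCS arm moved on both measures. The exposure is greatest when the trial's other hypotheses are true.

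**Working it through.** **The plan's own figures.** No power or error rate is stated for 3d or 3e. The Power paragraph assumes 75 per arm, alpha .05, d=.5 and a correlation of .5 between repeated measures, and concludes that power "is good to excellent (1- β = .80 and .99, respectively"). A two-sample t-test with 75 per arm, d=.5 and two-sided alpha .05 gives .86, not .80. A paired test within one arm of 75 gives .99. The mismatch at .80 is a separate matter and does not bear on this point. Only the inputs are used below.

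**Inputs.**
- N=150, 75 per arm (Power).
- Total sleep time by actigraphy in about 90 participants (Subjects).
- Two-sided alpha .05. Data Management and Analysis sets .05 for primary hypotheses. No level is set for 3d, so this is an assumption.
- Between-arm effect on pain: "The effect-size associated with clinical effects of tDCS on chronic pain in the current literature is also medium/modest (d=.5"). With the plan's r=.5 between repeated measures, the SD of a change is SD x sqrt(2(1-.5)) = SD, so d=.5 carries over to change scores.
- Between-arm effects on connectivity, COMM and total sleep time are not given. Values from .3 to .8 are assumed. The only imaging effect size in the plan, 1.8, is for pain minus rest and is not an arm difference.

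**Pooled correlation when the within-arm correlation is zero.** With equal arms and shifts d1 (connectivity) and d2 (outcome) in within-arm SD units, the between-arm covariance is d1·d2/4 and the pooled variances are 1+d1²/4 and 1+d2²/4. Hence

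r = (d1·d2/4) / sqrt[(1+d1²/4)(1+d2²/4)].

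For d1=d2=.5: r = .0625/1.0625 = .059.

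**Chance of p<.05.** On Fisher's scale the mean of the test statistic is m = atanh(r)·sqrt(N-3), and the rejection rate is P(Z > 1.96-m) + P(Z < -1.96-m). For r=.059 and N=150, m = .0589 x sqrt(147) = .714. The rate is P(Z > 1.246) + P(Z < -2.674) = .106 + .004 = 11.0%.

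| d on connectivity | d on outcome | pooled r | N=150 | N=90 |
|---|---|---|---|---|
| .3 | .3 | .022 | 5.8% | 5.5% |
| .5 | .3 | .036 | 7.2% | 6.3% |
| .5 | .5 | .059 | 11.0% | 8.5% |
| .8 | .5 | .090 | 19.5% | 13.4% |
| .5 | 0 | 0 | 5.0% | 5.0% |

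Simulation with 40,000 trials per row agrees to within half a percentage point (for example 19.8% for .8 and .5 at N=150). With arm removed from both variables, the simulated rate is about 5% in every row.

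**Sensitivity at .5 and .5.** With N=120 the rate is 9.8%. At alpha .01 and N=150 it is 3.2% against a nominal 1%, so a stricter threshold shrinks the inflation but does not remove it.

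**The case against.** The strongest reply is that the plan does not say it will pool. A reader might infer a decision to ignore arm. The text is only silent, and an analysis that includes arm would be consistent with it. That stands: the defect is an analysis left open, and the rates above apply only if the correlation is run as literally written.

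A reader might also infer that the trial could announce an association that does not exist between individuals. That goes too far. The pooled correlation is a real marginal association. What may be absent is the association within arms, and a false positive here means false with respect to that within-arm question.

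The size should not be overstated either. A pooled r of .06 explains about 0.35% of variance, well below the |r| of about .16 needed for p<.05 at N=150. Both variables must shift by arm. N=150 assumes that everyone has both scans and both outcome measurements, and the plan gives no dropout figure. Large connectivity effects have no basis in the documents, and smaller ones give rates close to nominal.

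Counting the chance that at least one of the three correlations in 3d is significant would make the problem look bigger. Most of that is multiplicity: three independent tests at .05 already give 1-.95³ = 14% with arm in the model, and adding arm does not change that.

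These points limit the size. They do not remove the gap, because the plan's own hypotheses predict the condition that creates the artefact, and leaving the model open allows the choice to be made after the data are seen.

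**Conclusion.** The point holds in a limited form. Hypotheses 3d and 3e state a correlation of changes with no arm term, and nothing elsewhere in the plan supplies one. Since the plan expects real tDCS to move connectivity and the clinical outcomes, a simple correlation over all participants could not be read as evidence of mechanism independent of the arm effects.

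At d=.5 on both variables the error rate for one outcome roughly doubles with 150 complete participants. It stays near nominal for effects of .3 and approaches 20% only if the connectivity effect is about .8. These figures assume zero within-arm correlation, equal arms, complete scans and two-sided alpha .05. Every connectivity effect used is an assumption.

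A reader might infer that the trial's efficacy findings are at risk. They are not: the weakness is confined to the mechanistic aim.

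**What to change.** In Hypotheses 3d and 3e, replace the unspecified correlation with a regression of each clinical change on connectivity change that includes arm, or equivalently a partial correlation pooled within arms. Report the connectivity coefficient with its 95% CI, and show the estimates for each arm alongside. If an unadjusted correlation is also wanted, label it as descriptive.

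This takes a sentence or two in the analysis plan and one degree of freedom per model. It needs no new data, scans or visits.

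### Connectivity from the pain/rest block scan is not separated from the evoked pain response, so H3c, H3d and H3e can move with activation, in either direction, without a change in coupling

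*Combined protocol and SAP*

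**What the plan says.** Neuroimaging Procedures describes one functional paradigm: "This temperature will be delivered in 12-second tonic blocks interspersed with 18-second rest/pain rating periods during the fMRI sequence". On processing it says "The data will be preprocessed in accordance with standard practice in our laboratory using SPM 8", with "the average time courses from anatomically defined regions of interest (ROIs) extracted and analyzed using customized scripts". The steps are not itemised. The fMRI paragraph under Power describes the study as well powered "using the pain-rest block paradigm and functional connectivity methods proposed", which ties connectivity to the block scan. No resting-state run is described.

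The paragraph after Hypothesis 3d defines the second dependent variable as "functional connectivity (quantified as the average correlation coefficient between the ROIs) between the left DLPFC and the aforementioned ROIs". No task regression, partial correlation, psychophysiological interaction or restriction to one condition is mentioned.

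Hypothesis 3b reads: "After treatment, percent BOLD signal change in the left DLPFC during pain blocks will be significantly greater in the CBT + real tDCS group". Hypotheses 3c and 3e then predict greater DLPFC connectivity with insula and ACC in the same arm at the same time point. Hypotheses 3d and 3e relate the change in connectivity to pain, opioid severity and sleep time. These are listed as hypotheses distinct from 3b.

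The one built-in check is: "We will also investigate the functional connectivity with a negative control region (i.e., the primary visual cortex), which should not be differentially" affected by either treatment.

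Two other places bear on direction. The section Brain Pathways in Pain and Addiction expects DLPFC activation to dampen the ACC and insula response to pain, and Hypothesis 3a expects an inverse DLPFC-limbic relation at baseline.

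**The concern.** Two regions that both follow a 30-second heat/rest cycle will correlate because they share the timing, even if nothing else links them. If real tDCS changes how strongly one of them responds to heat, the correlation changes too. Followed as written, the plan counts that shared response as coupling.

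The interpretation of Aim 3 is at stake. The plan uses this quantity to test whether CBT and tDCS act synergistically on pain-control circuitry. A positive H3c could be H3b reported a second time as a mechanism. A null H3c could be a real coupling gain offset by a fall in the limbic response. H3d inherits the problem person by person, because an individual's change in the correlation mixes change in activation with change in coupling.

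**Working it through.** **The plan's own figure.** The plan gives no figure for connectivity. Its only fMRI calculation is for pain-minus-rest activation: effect size 1.8, 12 per group, two-tailed alpha .01, power .80. Read as a standardised two-group difference, those inputs give power .93 (noncentral t), so the stated value is conservative on that reading. Nothing below depends on it.

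**Inputs.** From the documents: 12 s heat and 18 s rest/rating (30 s cycle), and 75 per arm. Assumed, because the documents do not give them: TR 2 s, 12 cycles, true coupling rho = .2 in both arms (between-person SD .15 on the Fisher-z scale), and the share f of each region's variance that is due to the blocks.

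**Formula.** With block shares f1 (DLPFC) and f2 (target), and coupling rho between the remaining signals:

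r = rho × √((1−f1)(1−f2)) + √(f1 × f2)

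The comparison state is f1 = .10, f2 = .40: r = .2 × √(.90 × .60) + √.04 = .147 + .200 = .347. With coupling held at .2:

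| Change in the real arm | f1, f2 | r |
|---|---|---|
| DLPFC up only | .15, .40 | .143 + .245 = .388 |
| DLPFC up only | .20, .40 | .139 + .283 = .421 |
| DLPFC up, insula down | .15, .25 | .160 + .194 = .353 |
| DLPFC up, insula down | .20, .20 | .160 + .200 = .360 |
| DLPFC up, insula well down | .20, .10 | .170 + .141 = .311 |
| Insula down only | .10, .25 | .164 + .158 = .322 |
| Insula down only | .10, .20 | .170 + .141 = .311 |

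**Direction.** Write a and b for the evoked amplitudes of DLPFC and target, each relative to its own noise SD. Then r rises with a only if b > rho × a. A target that responds weakly, deactivates or is dampened gives a flat or falling correlation.

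**False arm differences** (simulated two-sample test on Fisher z, alpha .05, no change in coupling):

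- DLPFC up, insula unchanged, same amplitude in everyone: 55% (share .15) and 97% (share .20).
- The same, with between-person amplitude CV .5: 26% and 64%. The value .5 is close to 1/1.8 = .56, which holds if the plan's 1.8 is a mean divided by an SD.
- The same, with CV .75: 13% and 34%. With a target share of 15% and CV 0: 18% and 45%.
- DLPFC up and insula down (.15/.25 and .20/.20): about 6% and 10%.
- Insula down only (.10/.25 and .10/.20): about 23% and 39%, with the real arm lower.
- First two DLPFC scenarios after regressing out the block response: 4% to 5%.

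**Second parametrisation.** This used 240 volumes, AR(1) noise of .3, an extra between-person SD of .2 on z, DLPFC amplitude doubling from 0.5 to 1.0 noise SD, and coupling of 0, .2 or .4. With a target amplitude of 0.5 to 1.0, the raw correlation differs falsely in 9% to 60% of trials. After regression the rate is 4.2% to 5.6%, and mean r stays at its true value.

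**The control region.** In that second set-up, a target with no heat response and coupling .2 goes from .196 to .184. It would look unaffected while the insula correlation (target amplitude 1.0) goes from .263 to .325.

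**The case against.** The strongest reply is that the protocol does not predict a DLPFC rise on its own. It expects the limbic response to fall as DLPFC rises, and in that joint scenario the bias nearly cancels (about 6% to 10% against a nominal 5%). This stands, and it rules out a reading that a reader might be tempted by: that any rise in DLPFC activation must appear as a rise in connectivity. The sign condition shows otherwise. But cancellation depends on the two changes being of matching size. An insula fall alone biases the test the other way, against H3c.

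Second, task removal may already be part of the laboratory's standard preprocessing or its custom scripts. A reader might infer that the plan commits to an unadjusted correlation. It does not say so; the step is unstated, neither described nor excluded. Unadjusted correlation remains the natural reading of the definition, and a pre-specified outcome should not turn on an undescribed script.

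Third, the largest rates are a corner case: everyone has the same response amplitude, the insula share is 40%, and alpha is .05. The fMRI sections use .01. At that level the two DLPFC-only scenarios give about 27% and 91% with fixed amplitudes, and 10% and 39% with CV .5. So the documents do not support a claim that most trials would give a false result.

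Fourth, a reader might infer that specificity will be declared when the target is significant and visual cortex is not. The plan states no such rule; it says only that the control connectivity will be examined.

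Finally, Aim 3 is mechanistic, and the primary outcomes listed under Data Management and Analysis include no fMRI measure. That limits the consequence to the mechanistic conclusions.

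**Conclusion.** The point holds in this form. Connectivity is defined as a correlation of ROI time courses from a block scan, with no stated removal of the evoked response, so H3c, H3e and the H3d correlations cannot be read as evidence separate from activation. The bias may create an apparent gain, hide a real one or roughly cancel. The visual-cortex check does not protect against it if that region does not respond to heat.

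The mechanism and its sign condition follow from the definition. The sizes do not, because they rest on assumed block shares, coupling, TR, run length and between-person variation. At alpha .05 the worked cases give about 25% to 97% for a DLPFC rise with an unchanged insula response (lower still with more variable amplitudes or a weaker target), about 6% to 10% with accompanying insula attenuation, and about 23% to 39% in the opposite direction for insula attenuation alone. Removing the block response brings the rate to about 5%. These are illustrations, not bounds. The clinical outcomes are unaffected. The plan should be changed, because a better-defined measure is available from the same scans.

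**What to change.** In the paragraph after Hypothesis 3d, define connectivity as the Fisher-z correlation of ROI time courses after regressing out HRF-convolved pain-block and rating-period regressors. Test H3c, H3d and H3e on that quantity, for DLPFC-insula and DLPFC-ACC, and report the H3b activation result beside it so that the two can be read together.

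State when the rating occurs within the 18 s. If it fills the whole interval, its regressor is the complement of the pain block, and the pain regressor with an intercept already covers both. If the laboratory's scripts already remove the task response, one sentence saying so settles the point.

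A direct arm comparison of target-minus-visual-cortex connectivity would be a useful addition but is optional.

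The cost is SAP wording and a small script change, with no new scans. Where regions share the block response, connectivity values will be smaller than raw correlations.
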